9.5 Handling of Missing Data

9.5.1 Handling of Missing Efficacy Data

If a patient prematurely discontinues clinical trial participation for any reason apart death, re-transplantation or withdrawal of consent, he/she will be encouraged to complete the follow-up. All observed available data will be used for the primary **CCI** analyses. The assumption of the LMM (section 14.1) for missing data will be MAR. Since the definition of progression of BOS

includes all relevant intercurrent events (IEs) as failures, drop-outs due to other reasons will be treated as non-informative censoring (section 14.3.2).

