#### 12.1.2 Progression of BOS

Due to the patchy distribution of affected areas in the pulmonary allograft, chronic rejection and BOS are not uniformly detectable by biopsy. This method has turned out to be too unspecific and harmful for routine diagnostic use. Therefore, non-invasive spirometry has been routinely

---

established using standardized airflow measurements which nowadays is used to determine FEV1 as a surrogate marker for the diagnosis of BOS, its classification and its control of progression.

Progression of BOS during the treatment period is defined as a decline of FEV1 of  $\geq 10\%$  or  $\geq 200$  mL from Baseline FEV1 and absolute decrease in FEV1/FVC of  $> 5\%$  that is confirmed by measurements that are taken with **CCl** spirometer at least 2 weeks apart OR worsening in BOS Severity grade OR Re-transplantation, OR Death from respiratory failure.

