### 15.2.3 Analyses of Efficacy

#### 15.2.3.1 Primary endpoint

##### *Analysis population and estimand*

FEV1 data collected from the on site **CCI** spirometer will be considered primary, while the data collected with the **CCI** home spirometer will be used for supportive analyses.

The primary efficacy parameter is the difference in mean FEV1 change from baseline to Week 48 between L-CsA plus SoC and SoC alone in the FAS population. Intercurrent events will be ignored, in line with the “treatment policy strategy” (ICH E9 addendum on estimands and sensitivity analysis in clinical trials to the guideline on statistical principles for clinical trials). After intercurrent events such as stopping treatment with L-CsA, augmentation of SoC therapy etc., FEV1 measurements will still be collected and used in the analysis. Intercurrent events preventing the use of FEV1 measurements after the event are death, re-transplantation, and withdrawal of the patient’s consent. It is anticipated that these events will be rare in this patient population. The estimand will be estimated as if these events had not happened, i.e., the unobserved FEV1 data of such patients will be modeled until the scheduled end of treatment at Week 48.

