8 STATISTICAL CONSIDERATIONS

8.1 General Considerations and Descriptive Statistics

All report outputs will be produced using [REDACTED] version 9.2 or later, in a secure and validated environment. All tables, figures and data listings (TFLs) to be included in the report will be independently checked for consistency and integrity.

The data recorded in the eCRF will be summarized as appropriate, per treatment group and for the total group, using the following descriptive measures:

- All continuous variables will be summarized using descriptive statistics (i.e., n, mean, standard deviation (SD), median, Q1, Q3, minimum, and maximum).
- All categorical variables will be summarized by using frequency counts and percentages.
- Discrete ordinal or higher-level data will be summarized as continuous data, but a tabulation of categories may also be included, depending on the number of categories.
- For time-to-event variables, cumulative event-free survival times will be evaluated using the Kaplan-Meier method. A frequency table showing the number of events and censored patients by treatment group, will be presented along with the event-free rates (and two-sided 95% confidence). Kaplan-Meier graphs will be presented along with the number of patient-at-risk at exact time points. If different rules are not specified, patients who are free from event will be censored at the study termination.

For all measures analyzed descriptively (i.e., measures to characterize the treatment groups and their baseline status, efficacy, and safety outcomes), tabulations comparing the treatment groups will be prepared. For outcomes measured more than once, the analyses will include tabulations of the measured values by visit, as well as change from baseline. Where provided, all confidence intervals will be two-sided 95% intervals.

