14.1 PRIMARY EFFICACY ANALYSIS

14.1.1 Analysis Population and Estimand

The primary endpoints will be analyzed using a “composite strategy” (International Conference on Harmonization (ICH) guideline E9 addendum on estimands and sensitivity analysis in clinical trials to the guideline on statistical principles for clinical trials). The estimand is defined by the following:

- Population: adult recipients of a single pulmonary allograft with clinically defined BOS, matching the inclusion and exclusion protocol criteria.
- Variable: FEV₁ data at Week 48 (visit 9) collected from the on site **CCI** spirometer (data collected with the **CCI** home spirometer will be used for supplementary analyses). Only accepted over-reader best FEV₁ data for the session from **CCI** will be used for analysis; data will not be re-derived.
- Intercurrent events: After IEs such as stopping treatment with L-CsA, augmentation of SoC therapy, etc., FEV1 measurements will still be collected and used in the analysis. In case of IEs preventing the use of FEV1 measurements, i.e. death and re-transplantation, the FEV1 will be imputed as treatment failure: FEV1 equal to zero for all visits subsequent the event. Rejected spirometries are those that did not meet the American Thoracic Society criteria; if rejected, then they would be re-done but there may be cases where they are rejected twice and resulting in missing data. Rejected spirometry is not an indicator of a better/worse outcome and can be assumed to be MAR.

- Population-level summary: difference in mean change from baseline in the FEV₁ at week 48 between treatment groups.

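### SAP 9.5.1 justifies non-informative censoring by a claim that the readable definition of BOS progression does not support: only death from respiratory failure counts as an event

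*SAP*

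**What the plan says.** SAP 9.5.1 gives a reason and a rule in one sentence. The definition of progression "includes all relevant intercurrent events (IEs) as failures, drop-outs due to other reasons will be treated as non-informative censoring", with a pointer to SAP 14.3.2, which is redacted.

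The readable definition is in Protocol 12.1.2. It starts with a confirmed spirometric decline and continues "OR worsening in BOS Severity grade OR Re-transplantation, OR Death from respiratory failure". No other death is listed.

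The general rule for time-to-event variables in SAP 8.1 is Kaplan-Meier, with this default: "If different rules are not specified, patients who are free from event will be censored at the study termination".

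Elsewhere death is not restricted by cause. Protocol 15.2.3.1 names death, re-transplantation and withdrawal of consent as the intercurrent events after which FEV1 cannot be used. SAP 14.1.1 says that for the events that prevent use of FEV1, "i.e. death and re-transplantation, the FEV1 will be imputed as treatment failure: FEV1 equal to zero for all visits subsequent the event". The protocol synopsis plans to assess overall, BOS-related and non-BOS-related mortality, so deaths outside the progression definition are foreseen.

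Protocol 9.3.1 leaves treating physicians unblinded. SAP 8.5 provides a blinded Adjudication Committee for progression data but gives the investigator the final decision on whether an event is BOS progression.

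**The concern.** The SAP does not simply assume that censoring is non-informative. It derives the assumption from the statement that every relevant intercurrent event is already a failure. If deaths from infection, malignancy or renal failure are outside the definition, that statement is untrue and the derivation falls with it.

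Three things follow on the readable text:

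- **Wrong quantity.** A patient who dies of another cause cannot progress later. Censoring that death makes Kaplan-Meier assume that the patient would have progressed at the rate of those still followed. The result is neither the share who progressed nor the share alive without progression.
- **Two treatments of one death.** A death from, say, malignancy is a failure in the primary FEV1 analysis and a censored observation in time to progression. SAP 9.5.1 gives no reason for the difference, because it claims that there is none.
- **The label carries weight.** In a patient with BOS, a fatal pneumonia may be recorded as respiratory failure or as infection. In an open-label trial that choice decides between event and censoring.

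**Working it through.** No event count, hazard ratio or power for time to BOS progression is readable, so there is no plan figure to reproduce. The sample-size figures in Protocol 15.5 (200 mL, SD 350 mL, 50 per arm) concern FEV1 only.

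**Step 1: compare the texts.** Intercurrent events named in Protocol 15.2.3.1 against the events in Protocol 12.1.2:

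| Intercurrent event | Failure under 12.1.2? |
|---|---|
| Re-transplantation | Yes |
| Death from respiratory failure | Yes |
| Death from another cause | No |
| Withdrawal of consent | No |

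The claim of completeness in SAP 9.5.1 fails on two rows.

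**Step 2: effect on one arm's curve.** Inputs: 62 randomized (SAP 8.2), so about 31 per arm. The numbers of progressions (P) and non-respiratory deaths (D) are assumed, because the documents give none. There is no other censoring before Week 48.

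- Competing event: proportion not progressed = 1 − P/31. This includes patients who died without progressing.
- Deaths censored: Kaplan-Meier, the product of (1 − 1/number at risk) over progressions. If all deaths come last it is (31 − P)/31. If all come first it is (31 − D − P)/(31 − D). The table gives the average over random event orders.
- Alive and progression-free: 1 − (P + D)/31.

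| P, D | Competing event | Censored: deaths first to last | Censored: average | Alive and progression-free |
|---|---|---|---|---|
| 5, 3 | 26/31 = 83.9% | 23/28 = 82.1% to 83.9% | 83.0% | 23/31 = 74.2% |
| 8, 3 | 23/31 = 74.2% | 20/28 = 71.4% to 74.2% | 72.7% | 20/31 = 64.5% |
| 5, 2 | 26/31 = 83.9% | 24/29 = 82.8% to 83.9% | 83.3% | 24/31 = 77.4% |

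Censoring minus competing event: −0.9, −1.5 and −0.6 points. Progression-or-death endpoint minus censoring: −8.8, −8.2 and −5.9 points. The second gap is close to the assumed deaths themselves (3/31 = 9.7%, 2/31 = 6.5%).

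**Step 3: effect on the treatment contrast.** Assume constant, independent hazards over 48 weeks: h = −ln(1 − progression risk), d = −ln(1 − other-death risk). The progression hazard ratio (L-CsA over SoC) is h_L/h_S. It is the same whether other deaths are called censored or competing. The progression-or-death hazard ratio is (h_L + d_L)/(h_S + d_S).

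With assumed progression risks of 30% and 40%, h_L = 0.357 and h_S = 0.511, so the progression hazard ratio is 0.70.

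| Other-death risk, L-CsA vs SoC | Progression-or-death hazard ratio |
|---|---|
| 3% vs 3% | 0.387/0.541 = 0.72 |
| 10% vs 10% | 0.462/0.616 = 0.75 |
| 10% vs 3% | 0.462/0.541 = 0.85 |
| 13% vs 3% | 0.496/0.541 = 0.92 |
| 3% vs 10% | 0.387/0.616 = 0.63 |

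On the risk scale, the difference by one minus Kaplan-Meier is 40.0% − 30.0% = 10.0 points. By cumulative incidence it is 39.4% − 28.6% = 10.8 points for other-death risks of 10% vs 3%, and 38.1% − 29.6% = 8.5 points for 3% vs 10%.

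With risks of 18% and 50%, patterned on study AI001 (Protocol 7.1.4), the progression hazard ratio is 0.29. The progression-or-death ratio is 0.32 to 0.38 for equal other-death risks of 3% to 10%, 0.42 for 10% vs 3%, and 0.29 for 3% vs 10%.

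**The case against.** The strongest objection is that the governing text cannot be read. Protocol 15 makes the final SAP the analysis of record, and SAP 14.3.2 may count more deaths or use a competing-risk method. The visible trail settles nothing. The version history extends the zero-FEV1 imputation to several sections and not to 14.3.2, but a time-to-event section has no FEV1 to impute, and several items in SAP 16 are redacted. This objection stands, and the point is conditional for that reason. What it does not rescue is the mismatch between the stated rationale and the only readable definition.

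A reader might infer that censoring flatters the L-CsA curve by 9 points. It does not. That gap compares two different endpoints. A censored death does not raise a Kaplan-Meier curve, and against competing-event handling the censored estimate is slightly lower.

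A reader might also infer that the two endpoints must treat death alike. They need not. A disease-specific endpoint may count only respiratory death while a lung-function composite counts all deaths, and other mortality is assessed separately. Replacing the main definition with all-cause death would be a debatable trade-off and would alter a protocol-defined endpoint.

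Nor do the documents show that L-CsA causes the deaths in question. Protocol 7.1.3 and 7.1.4 report no increased risk of nephrotoxicity, respiratory infection or malignancy to date, and Protocol 15.2.3.1 expects death to be rare.

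The blinded committee reduces the labelling concern but does not remove it, because SAP 8.5 leaves the final decision with the investigator.

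**Conclusion.** The concern holds in limited form. The rationale in SAP 9.5.1 is not supported by Protocol 12.1.2. Unless SAP 14.3.2 says otherwise, non-respiratory deaths would be censored as non-informative. It cannot be stated as fact that they will be.

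Under the assumed counts (31 per arm, 2 or 3 such deaths), the choice between censoring and competing-event handling is worth about 0.6 to 1.5 points per arm. The separate progression-or-death estimate would be about 6 to 9 points lower than the censored one. Its treatment contrast stays close to the progression contrast if such deaths are rare and balanced (0.72 against 0.70 at 3% in each arm). It moves materially when they are imbalanced (0.63 to 0.92 in the same scenario).

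SAP 14 makes all analyses descriptive, and the protocol synopsis keeps the testing hierarchy for time to progression only within the double-lung study. No confirmatory conclusion here depends on the point. The descriptive curves should still estimate a clearly defined quantity.

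**What to change.** 1. In SAP 9.5.1, delete the statement that the definition already covers all relevant intercurrent events, or correct it to name those it covers. Make it agree with SAP 14.3.2.
2. Keep the protocol-defined endpoint. Handle non-respiratory death as a competing event: cumulative incidence of progression by arm, with cause-specific hazards for the comparison.
3. Add a sensitivity analysis of time to BOS progression or death from any cause. It does not depend on whether a death is labelled respiratory.
4. Apply non-informative censoring only to patients last known alive. This still includes withdrawals of consent, so state it there as an assumption and not as a consequence of the definition.

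The cost is a change of SAP wording and one or two extra analysis runs. Protocol 12.1.5 already requests the cause of death, so no new data are needed, and the protocol endpoint is unchanged. If SAP 14.3.2 already handles other deaths in one of these ways, only item 1 remains.

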9.5.2 Handling of Missing Safety Data

In general, missing clinical laboratory data, vital signs, and physical examination data will not be imputed. Unknown or partial medication and AE date imputations are given in the next section and to be used only for the assessment of prior/concomitant status for medications and treatment-emergent status for AEs.

9.5.3 Handling of Partial and Missing Dates

9.5.3.1 Partial and Missing Dates of Birth

Only the year is recorded for the Date of Birth, therefore there will not be any imputation.

9.5.3.2 Missing or Partial AE and Prior / Concomitant Medication Start and End Dates

Missing and/or incomplete dates for medications and AEs are imputed in a manner resulting in the earliest onset or the longest duration during the Treatment Period, whilst ensuring that the start date does not occur after the stop date.

For the derivation of the duration and cumulative of concomitant medication, if the medication is “Ongoing” then the medication end date will be imputed with the last visit date.

The stop date will not be imputed if the AE is “Ongoing”. Technically, this will be done as follows:

- For a missing/incomplete start date/time, the earliest date/time of the following will be imputed:
 - The later date / time of: the earliest possible start date/time and the date/time of first dose of treatment (date/time of randomization).
 - The latest possible start date/time.
- For a missing/incomplete stop date/time, the later date/time of the following will be imputed:
 - The earlier date/time of: the latest possible stop date/time and the date/time of last dose of treatment (date/time of study completion or early termination).
 - The earliest possible stop date/time.
- Here, the earliest possible date/time is defined as:
 - The date/time itself if available.

- The date/time of the first day of the month at 00:00hrs, if month and year are available but the day/time is missing.
- The date/time of the first day of the year at 00:00hrs, if year is available but day/time and month are missing.
- 00:00hrs on the day of informed consent, if the date/time is completely missing.
- The latest possible date/time is defined as:
 - The date / time itself if available.
 - The date / time of the last day of the month at 23:59hrs, if month and year are available but the day / time is missing.
 - The date / time of the last day of the year at 23:59hrs, if year is available but day / time and month are missing.
 - 23:59hrs on the date of last known date on the study for the patient plus one year, if the date / time is completely missing.

10 DISPOSITION

The number of patients screened, failed screening (patients who did not meet all eligibility criteria and was not randomized), enrolled (patients with informed consent and all eligibility criteria met or randomized), treated but not randomized, randomized (treated, and not treated with clinical trial treatment), completing clinical trial treatment (and reasons for not completing), and completing the clinical trial (and reason for not completing) will be presented in frequency tables by treatment group.

The number of patients in each analysis population (SAF, FAS, and PPS) will be summarized by treatment group. A by-patient listing of disposition will be provided.

All major protocol deviations will be presented as a frequency table by treatment group and in a by-patient listing for all randomized patients, which will include the category of the deviation, the deviation text, and whether the patient was excluded from PPS.

In addition, the counts on major COVID-19 related PDs will be provided, together with a by-patient listing for all COVID-19 related PDs.

In addition, a listing of the patients affected by Coronavirus Disease of 2019 (COVID-19) and their COVID-19 AE details will be provided for the FAS.

A table for the summary of stratification factors by treatment group for FAS and a separate listing of patients with mis-stratifications will be displayed.

11 DEMOGRAPHICS AND BASELINE CHARACTERISTICS, AND DISEASE AND MEDICAL HISTORY

11.1 Demographic and Baseline Characteristics

All demographic, baseline characteristics, including azithromycin at randomization, and antibody-response data will be summarized by treatment group for SAF, FAS and PPS. For summary purposes, the most recent, non-missing result obtained on or prior to the baseline visit will be used.

Azithromycin at randomization will be derived by identifying azithromycin among medications collected in the study (generic name: azithromycin) using any of the following rules:

- azithromycin is ongoing at the date of randomization (regardless of start date)
- azithromycin start date is on the randomization date (regardless of end date)

By-patient listings will be provided for all demographic and baseline characteristics.

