#### 9.3.1 Blinding

The pulmonary function technicians, respiratory therapists, or physiotherapists who conduct spirometry on site will be blinded to treatment assignment. Patients and other unblinded personnel will be asked to not share treatment assignment information with the pulmonary function technicians, respiratory therapists, and physiotherapists. For details of the blinding of the Data Monitoring Committee members, see [Section 13.2](#). For details of the blinding of the Adjudication Committee members, see [Section 13.3](#). Clinical trial monitors, treating physicians, study nurses, study coordinators, and enrolled patients will not be blinded to treatment assignment.

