### 11.3 Concurrent Treatment or Medication

All participants randomized, whether enrolled in the L-CsA arm plus SoC arm or Standard of Care arm of this protocol, will receive standard of care therapies for the maintenance of their allograft. SoC includes maintenance immunosuppressive medication, prophylaxis against common opportunistic infections, and all other necessary medications and therapies for the optimal care of the patient. This also include vaccination against CoV-SARS 2. Changes to immunosuppression and use of azithromycin are also considered SoC. All changes in the concurrent treatment or medication will be administered according to site's standard of care.

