14.1.3 Analysis Model

The primary efficacy analysis will be carried out using a LMM for repeated measurements, using all observed available FEV₁ measurements. In case of death or re-transplantation events, FEV₁ will be imputed as zero at each nominal day post event.

The dependent variables are the absolute change from baseline of FEV₁ measurements at visit 2 (i.e., the first post-baseline visit) through visit 9 (Week 48). For the definition of baseline FEV₁ please refer to section 8.1.1.

A flexible and robust model will be chosen for the random part of the LMM according to a pre-specified stepwise procedure (see next section). The original protocol considered the fixed part of the LMM containing the following (except from the intercept): time cubic splines, treatment, the interactions of time splines by treatment, baseline FEV₁, the interactions of time splines with the baseline FEV₁, region (North America versus all other countries together), underlying indication for lung transplant (COPD versus all others), and use of azithromycin at randomization (i.e. Baseline, Visit 1). Due to the reduced sample size (see section 8.2), the covariates will be selected taking into account model convergence (as detailed below).

The primary efficacy parameter will be estimated from the model by the adjusted difference between treatment groups in mean FEV₁ change from baseline after 48 weeks. The p-value for the null hypothesis of no difference and a two-sided 95% confidence interval for the difference will be provided. The comparison between treatment groups at all the other visits (2-8) will also be presented.

A figure of observed mean change from baseline and standard errors at each visit, by treatment group will be presented. A figure with adjusted mean changes from baseline at each visit by treatment group derived from the LMM will be provided.

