14.1.4 Specification of the Model

For valid inference on the primary efficacy parameter, the evolution of FEV_1 in both treatment groups should be modeled as a flexible function in time, without unnecessarily strong assumptions.

Therefore, time will be modeled assuming that the time evolution of FEV_1 is a smooth function of time. Cubic splines will be used with a large enough number of parameters to minimize the risk of misspecification. We will choose one knot at 182 days, i.e., halfway between the first (day 28) and the last scheduled measurement (337 days). So, it is assumed that the mean of FEV_1 is a third-degree polynomial at each of the two intervals, smoothly connected, equal at day 182 with equal first and second derivative. Thus, 4 parameters per group are used to model time. In total, as many as 12 parameters in the model will involve time, ensuring robust estimation of the time evolution of FEV_1 . Denoting the covariates associated with the splines by $S_1=t$, $S_2=t^2$, $S_3=t^3$ and $S_4=\max(t-182,0)^3$, the treatment group by T ($0=SoC$; $1=L-CsA$ plus SoC), the day of the measurement by t and the baseline FEV_1 by X , the fixed part of the model will contain the following covariates:

Intercept, $S_1, \dots, S_4, T, T*S_1, \dots, T*S_4, X, X*S_1, \dots, X*S_4$, other covariates

The Kenward-Roger adjustment will be used for the denominator degrees of freedom needed for hypothesis tests and confidence intervals.

The other covariates are:

- underlying indication for lung transplant (COPD versus all others)
- Region (North America versus all other countries together)
- Use of azithromycin at randomization.

In case of collinearity or non-convergence, covariates will be dropped in the above order, starting with the last. With the final selection of covariates in the model in place, the random part of the LMM will then be selected by comparing the Akaike Information Criterion (AIC) of three models:

- model with random intercept and random time;
- model with random intercept, random time and random squared time;
- model with random intercept, random time, random squared time, and random cubic time.

The model with the lowest AIC will be adopted for the primary analysis.

The core excerpt of **CCI** code for the primary analysis is reported in section 17.1.

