14.5 SUBGROUP ANALYSES

Analyses of primary CCI  endpoints will be performed on the following subgroups of patients:

- Age class (<55 years, \geq 55 years),
- Gender (female, male, undifferentiated),
- Region (North America, all other countries together),
- Severity of disease, defined by:
 - % of baseline FEV₁ over personal best FEV₁ post-transplant (baseline FEV₁ >80%, >65–80%, >50–65%, and \leq 50% of personal best FEV₁ post-transplant),
 - baseline FEV₁ % of predicted (<70%, \geq 70%),
 - baseline FEV₁/FVC ratio (< 0.7, \geq 0.7),
 - BLAD at time of personal best post-transplant FEV₁ (Yes, No);
- Race (American Indian or Alaskan Native, Asian, Black or African American, Native Hawaiian or Other Pacific Islander, White, Other).

- Use of azithromycin at randomization (Yes/No)

Subgroup levels may be pooled to have an adequate number (≥ 10) of patients per strata to perform the analysis. Decision on pooling will be taken during the blinded DRM, before data base lock.

Within each subgroup level, descriptive analyses (section 8.1) will be performed on:

- FEV₁,
- FEV₁/FVC,
- Time to Progression of BOS.

FEV₁ and FEV₁/FVC change from baseline will be compared using a two-sample t-test (assuming unequal variances) or, if the required assumptions are not met, a two-sample Mann–Whitney U test.

Comparison of time to progression of BOS curves among treatments will be performed with the log-rank test.

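### SAP 11.1 can code azithromycin begun on Day 1 after open-label allocation as baseline use, and so carry it into the primary model and a subgroup

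*SAP*

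**What the plan says.** SAP 11.1 sets the flag to yes if either of two rules is met. The first is "azithromycin is ongoing at the date of randomization (regardless of start date". The second is "azithromycin start date is on the randomization date (regardless of end date". Neither uses clock time, and neither requires the course to have begun before allocation.

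SAP 14.1.3 describes the covariate as "use of azithromycin at randomization (i.e. Baseline, Visit 1", so a baseline variable is intended. SAP 14.1.4 lists "Use of azithromycin at randomization" last among the other covariates of the primary linear mixed model. SAP 14.2.1 carries the same covariates into the ANCOVA. SAP 14.5 defines a subgroup by "Use of azithromycin at randomization (Yes/No"; the SAP version history shows that this subgroup was added in version 3.0.

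On conduct, Protocol 9.3 and SAP 7.2 give the allocation to the investigator at the baseline visit. Protocol 9.3.1 states that "treating physicians, study nurses, study coordinators, and enrolled patients will not be blinded to treatment assignment". Protocol 11.3 states that "Changes to immunosuppression and use of azithromycin are also considered SoC", and the synopsis leaves changes to standard of care, azithromycin included, to the investigator's discretion.

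**The concern.** A covariate used for adjustment, or a factor that defines a subgroup, should be fixed before allocation is known. On Day 1 the treating physician learns the arm and may then start azithromycin. A patient who was not taking it, and so was not bound by the 4-week stability requirement in inclusion criterion 5, would be coded as a baseline user on the strength of that decision.

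Two things follow. First, SAP 14.1.1 keeps FEV1 measurements after augmentation of standard of care, so any difference between arms in added treatment is meant to stay in the estimate. Adjusting for a flag that partly records such a difference works against that intent. Second, if Day-1 starts differ by arm, the Yes and No subgroups no longer compare like with like.

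The SAP is also out of step with itself. SAP 13 places medication starts before or after randomization by date and time, while SAP 11.1 uses the calendar day. A course begun an hour after allocation is a post-randomization start under SAP 13 and a baseline characteristic under SAP 11.1.

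**Working it through.** The plan states no figure on this point, so there is none to reproduce. The check has three parts.

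**1. Which courses the rules admit**

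| Course | Rule 1 (ongoing) | Rule 2 (start on the day) | Pre-allocation use? |
|---|---|---|---|
| Long-term, continuing | yes | no | yes |
| Begun Day 1 after allocation, continuing | yes, on a calendar-day reading | yes | no |
| Begun Day 1 after allocation, short course | unclear | yes | no |
| Long-term, record split by a Day-1 dose change | depends on how the old record is closed | yes (new record) | yes |

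The second row shows that deleting rule 2 alone is not enough. The fourth shows that rule 2 may at present capture some genuine users.

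**2. Incomplete start dates**

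SAP 9.5.3.2 imputes a start as min{max(earliest possible, randomization), latest possible}. Take randomization on 10 March 2021 as an example:
- Known only as March 2021: min{max(1 March, 10 March), 31 March} = 10 March 2021.
- Known only as 2021: min{max(1 January, 10 March), 31 December} = 10 March 2021.
- Fully missing: the earliest possible date is the consent date and the latest lies beyond the study, so the result is again 10 March 2021.

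All three would trigger rule 2. SAP 9.5.2 limits imputed medication dates to deciding prior or concomitant status, so it is unclear whether they reach this flag.

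**3. Size**

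SAP 8.2 gives 62 randomized, hence about 31 per arm at 1:1. One Day-1 start is 1/62 = 1.6% overall and 1/31 = 3.2% of an arm.

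Let p be the true proportion of pre-randomization users, and s0 and s1 the proportions of non-users who start on Day 1 in the SoC and L-CsA arms. The flagged proportion is then higher in SoC by (1 - p)(s0 - s1). In a large sample with true prior use balanced, replacing the true flag by the SAP flag moves the adjusted difference by

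shift = g × (1 - p)(s0 - s1),

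where g is the pooled within-arm slope of FEV1 change on the SAP flag. Equal start rates give a shift of 0.

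All inputs below are assumptions except the 200 mL treatment difference (Protocol 15.5): p = 50 to 80%; s0 = 5 to 20% with s1 = 0%; effect of a Day-1 start 0 to +100 mL; prognosis of the type of patient who would start 0 to -200 mL; established users against non-users -100 to +200 mL.

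- Lowest case: p = 0.5, s0 = 0.2, established users -100 mL, no start effect, no prognostic difference. The within-arm covariances are -25 and -20 and the flag variances 0.25 and 0.24, so g = -45/0.49 = -91.8. Shift = -91.8 × 0.5 × 0.2 = -9.2 mL.
- Highest case: p = 0.5, s0 = 0.2, established users +200 mL, start effect +100 mL, prognosis -200 mL. The covariances are 60 and 36, so g = 96/0.49 = 195.9. Shift = 195.9 × 0.1 = +19.6 mL.

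A simulation with 1,000,000 patients per setting gave -9.18 and +19.56 mL at these extremes, and about 0 with 10% starting in each arm. Over the same grid the treatment difference in the Yes subgroup moved by -33 to +67 mL, and in the No subgroup by -40 to +20 mL.

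These settings imply between 31 × 0.2 × 0.05 = 0.3 and 31 × 0.5 × 0.2 = 3.1 starters in the SoC arm.

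**The case against.** The best defence is that this is a coding edge case with no demonstrated occurrence, and that its reach is limited. SAP 14 declares all analyses descriptive. Azithromycin enters the primary model as a main effect only, and it is the most expendable covariate: "In case of collinearity or non-convergence, covariates will be dropped in the above order, starting with the last", and it is listed last. The supplementary t-test does not use it. By-patient listings of baseline characteristics and concomitant medication would let a reader find Day-1 starts. All of this stands and limits the consequence. It does not make the rule right, and the subgroup remains exposed even if the covariate is dropped.

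Four stronger readings are tempting, and the documents do not support them.

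- A reader might infer that every Day-1 start in an eligible patient must follow allocation, because users need 4 weeks of stable use. Inclusion criterion 5 covers azithromycin for prophylaxis or treatment of BOS, whereas SAP 11.1 has no limit by indication. A course for another reason begun earlier that day, a split record or an eligibility deviation could also produce a Day-1 date.
- A reader might infer that the starts would fall in the SoC arm. That is plausible, but no document says so. The sign of the shift reverses if they fall in the other arm.
- A reader might use the pooling minimum of 10 patients in SAP 14.5 to say that one patient is 10% of a subgroup. Pooling the two levels of this factor leaves no subgroup, so that figure does not apply.
- A reader might think that requiring a start strictly before randomization in both rules is a costless edit. It would empty rule 2, and it could turn long-term users with missing, partial or split start dates into non-users.

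**Conclusion.** The concern holds as a defect in the derivation. As written, SAP 11.1 lets a treatment decision made after open-label allocation count as a baseline characteristic in the primary model, the ANCOVA and one subgroup. It does not show that any estimate is biased, because the documents do not say whether anyone started azithromycin on Day 1.

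Bias in the adjusted difference needs start rates that differ by arm. The range of about -9 to +20 mL rests wholly on assumed inputs. Its upper end is about 10% of the planned 200 mL difference (19.6/200) and needs roughly three starters in one arm and none in the other. The subgroup differences are more sensitive on the same assumptions. Correcting the rule is worthwhile because it is cheap, not because the result is likely to turn on it.

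**What to change.** In SAP 11.1:

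1. Delete the second rule.
2. Limit the first rule to courses ongoing at randomization that are not known to have begun on or after the randomization date and time. If no time is recorded, use the date.
3. State that dates imputed under SAP 9.5.3.2 are not used for this flag.
4. Settle missing or partial start dates, and records split by a Day-1 dose change, at the blinded data review meeting before database lock, so that long-term users stay classed as users.
5. Count known Day-1 starts after allocation as concomitant therapy only.

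The change needs no new data and alters neither the sample size nor the model. Its cost is a small amount of blinded review of incomplete or split records.
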